Concerns have been raised about cardiovascular safety of rosiglitazone, based on the initial (2007) and the updated (2010) meta-analyses of clinical trials by Nissen and Wolski^{3,4} and a Medicare-based study by Graham et al.⁵ These studies provided evidence of an increased risk of several cardiovascular outcomes in users of rosiglitazone compared with users of other oral antidiabetic medications or placebo. The postmarketing RECORD trial, ordered by a regulator and sponsored by the manufacturer, GlaxoSmithKlein, published in 2010,⁶ showed no overall effect of rosiglitazone on the primary outcome of cardiovascular morbidity and mortality. The trial, however, has been criticized for methodological flaws, including open-label design, considerable selection bias, and possible irregularities in case adjudication.⁷

In response to the safety concerns raised in 2007, EMA emphasised the need for providers "to adhere to the restrictions for use in patients with cardiac disease", but advised patients "not to stop treatment with rosiglitazone and to discuss the medication with their doctor at their next regular visit."⁸ In 2007, EMA concluded "that the benefits of [...] rosiglitazone [...] in the treatment of type 2 diabetes continue to outweigh their risks."⁹ In January 2008, EMA added contraindications for rosiglitazone to its label.¹⁰ The Food and Drug Administration in the United States also issued a boxed warning. The proportion of rosiglitazone prescriptions among all diabetic medications except insulin dropped in the US from around 11% in March 2007 to 6% in July 2007 and to less than 3% in 2009.¹¹

Following the two 2010 publications,^{4,5} the EMA suspended rosiglitazone-containing drugs from the European markets, on 23 September 2010.¹² On 3 December 2010, the European Commission (EC) issued a suspension decision, noting that risk minimisation in form of label warnings and restricted use has not been clearly effective. The scientific discussion accompanying the suspension decision noted that persons with indications for rosiglitazone may have an a-priori higher risk of cardiovascular morbidity. Still, based on all available evidence, the EC concluded that rosiglitazone does not provide unique therapeutic benefits that outweigh the risks of cardiovascular outcomes.¹³

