3.6.2 Contraindications for use and off-label use

Prevalence of contraindicated or off-label use will be examined according to calendar time, where events marking relevant scientific publications and regulatory decisions will be marked. We will

report the number and proportion of patients prescribed rosiglitazone who had a diagnosis consistent with a contraindication for rosiglitazone use or with off-label use as defined in the Methods. We will provide the proportions in each country and over time. We will follow the analytic methods described above, provided that the sample size is large enough. At a minimum, use by patients with the additional contraindications (ischemic heart disease and/or peripheral vascular disease) listed in the 2008 press release¹⁰ will be examined in the periods before and after the publication of the press release including any prior diagnosis of liver disease, ischemic heart disease, cardiac failure, or acute coronary syndrome.

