Appendix 1. Codes used in data abstraction

Diagnostic codes used to Abstract the Danish National Registry of Patients and the Registry of Causes of Death

Disease/condition	ICD-8 code	ICD-10 code
Diabetes type 1	249.00; 249.06; 249.07; 249.09	E10.0, E10.1; E10.9
Diabetes type 2	250.00; 250.06; 250.07; 250.09	E11.0; E11.1; E11.9
Acute myocardial infarction	410	I21, I22, I23
Ischemic heart disease (acute and chronic)	411-414	I20, I24, I25
Congestive heart failure	427.09, 427.10, 427.11, 427.19, 428.99, 782.49;	I50, I11.0, I13.0, I13.2
Other cardiac disease	393–398, 400–404	I05–I09
Peripheral vascular disease	440, 441, 442, 443, 444, 445	I70, I71, I72, I73, I74, I77
Ischemic stroke	430-438 (cerebrovascular disease)	I63-64
Alcoholism	291, 303, 577.10, 571.09, 571.10	F10.1-F10.9, G31.2, G62.1, G72.1, I42.6, K29.2, K86.0, Z72.1
Obesity	277.99	E65-E66
Mild liver disease	571, 573.01, 573.04	B18, K70.0–K70.3, K70.9, K71, K73, K74, K76.0
Moderate to severe liver disease	070.00, 070.02, 070.04, 070.06, 070.08, 573.00, 456.00–456.09	B15.0, B16.0, B16.2, B19.0, K70.4, K72, K76.6, I85
Deep vein thrombosis	451.00	I81, I82
Pulmonary embolism	450.99	I26

ICD-8: http://www.sst.dk/Indberetning%20og%20statistik/Klassifikationer/SKS_download.aspx

ICD-10: <http://apps.who.int/classifications/apps/icd/icd10online/>

Diagnostic codes used to compute Charlson Comorbidity Index¹⁹

Disease	ICD-8 code	ICD-10 code
Myocardial infarction	410	I21;I22;I23
Congestive heart failure	427.09; 427.10; 427.11; 427.19; 428.99; 782.49	I50; I11.0; I13.0; I13.2
Peripheral vascular disease	440; 441; 442; 443; 444; 445	I70; I71; I72; I73; I74; I77
Cerebrovascular disease	430-438	I60-I69; G45; G46
Dementia	290.09-290.19; 293.09	F00-F03; F05.1; G30
Chronic pulmonary disease	490-493; 515-518	J40-J47; J60-J67; J68.4; J70.1; J70.3; J84.1; J92.0; J96.1; J98.2; J98.3
Connective tissue disease	712; 716; 734; 446; 135.99	M05; M06; M08; M09;M30;M31; M32; M33; M34; M35; M36; D86
Ulcer disease	530.91; 530.98; 531-534	K22.1; K25-K28
Mild liver disease	571; 573.01; 573.04	B18; K70.0-K70.3; K70.9; K71; K73; K74; K76.0
Diabetes type1	249.00; 249.06; 249.07; 249.09	E10.0, E10.1; E10.9
Diabetes type2	250.00; 250.06; 250.07; 250.09	E11.0; E11.1; E11.9
Hemiplegia	344	G81; G82
Moderate to severe renal disease	403; 404; 580-583; 584; 590.09; 593.19; 753.10- 753.19; 792	I12; I13; N00-N05; N07; N11; N14; N17-N19; Q61
Diabetes with end organ damage type1	249.01-249.05; 249.08	E10.2-E10.8

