C104z00 DIABETES MELLITUS WITH NEPHROPATHY NOS
C105.00 DIABETES MELLITUS WITH OPHTHALMIC MANIFESTATION
C105100 DIABETES MELLITUS, ADULT ONSET, + OPHTHALMIC MANIFESTATION
C105y00 OTHER SPECIFIED DIABETES MELLITUS WITH OPHTHALMIC COMPLICATN
C105z00 DIABETES MELLITUS NOS WITH OPHTHALMIC MANIFESTATION
C106.00 DIABETES MELLITUS WITH NEUROLOGICAL MANIFESTATION
C106.11 DIABETIC AMYOTROPHY
C106.12 DIABETES MELLITUS WITH NEUROPATHY
C106.13 DIABETES MELLITUS WITH POLYNEUROPATHY
C106100 DIABETES MELLITUS, ADULT ONSET, + NEUROLOGICAL MANIFESTATION
C106y00 OTHER SPECIFIED DIABETES MELLITUS WITH NEUROLOGICAL COMPS
C106z00 DIABETES MELLITUS NOS WITH NEUROLOGICAL MANIFESTATION
C107.00 DIABETES MELLITUS WITH PERIPHERAL CIRCULATORY DISORDER
C107.11 DIABETES MELLITUS WITH GANGRENE
C107.12 DIABETES WITH GANGRENE
C107100 DIABETES MELLITUS, ADULT, + PERIPHERAL CIRCULATORY DISORDER
C107200 DIABETES MELLITUS, ADULT WITH GANGRENE
C107z00 DIABETES MELLITUS NOS WITH PERIPHERAL CIRCULATORY DISORDER
C108y00 OTHER SPECIFIED DIABETES MELLITUS WITH MULTIPLE COMPS
C108z00 UNSPECIFIED DIABETES MELLITUS WITH MULTIPLE COMPLICATIONS
C109.00 NON-INSULIN-DEPENDENT DIABETES MELLITUS
C109.11 NIDDM - NON-INSULIN DEPENDENT DIABETES MELLITUS
C109.12 TYPE 2 DIABETES MELLITUS
C109.13 TYPE II DIABETES MELLITUS
C109000 NON-INSULIN-DEPENDENT DIABETES MELLITUS WITH RENAL COMPS
C109011 TYPE II DIABETES MELLITUS WITH RENAL COMPLICATIONS
C109100 NON-INSULIN-DEPENDENT DIABETES MELLITUS WITH OPHTHALM COMPS
C109111 TYPE II DIABETES MELLITUS WITH OPHTHALMIC COMPLICATIONS
C109200 NON-INSULIN-DEPENDENT DIABETES MELLITUS WITH NEURO COMPS
C109211 TYPE II DIABETES MELLITUS WITH NEUROLOGICAL COMPLICATIONS
C109300 NON-INSULIN-DEPENDENT DIABETES MELLITUS WITH MULTIPLE COMPS
C109400 NON-INSULIN DEPENDENT DIABETES MELLITUS WITH ULCER
C109411 TYPE II DIABETES MELLITUS WITH ULCER
C109500 NON-INSULIN DEPENDENT DIABETES MELLITUS WITH GANGRENE
C109511 TYPE II DIABETES MELLITUS WITH GANGRENE
C109600 NON-INSULIN-DEPENDENT DIABETES MELLITUS WITH RETINOPATHY
C109611 TYPE II DIABETES MELLITUS WITH RETINOPATHY

C109700 NON-INSULIN DEPENDANT DIABETES MELLITUS - POOR CONTROL
 C109711 TYPE II DIABETES MELLITUS - POOR CONTROL
 C109900 NON-INSULIN-DEPENDENT DIABETES MELLITUS WITHOUT COMPLICATION
 C109A00 NON-INSULIN DEPENDENT DIABETES MELLITUS WITH MONONEUROPATHY
 C109A11 TYPE II DIABETES MELLITUS WITH MONONEUROPATHY
 C109B00 NON-INSULIN DEPENDENT DIABETES MELLITUS WITH POLYNEUROPATHY

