C10F300 TYPE 2 DIABETES MELLITUS WITH MULTIPLE COMPLICATIONS
C10F400 TYPE 2 DIABETES MELLITUS WITH ULCER
C10F500 TYPE 2 DIABETES MELLITUS WITH GANGRENE
C10F600 TYPE 2 DIABETES MELLITUS WITH RETINOPATHY
C10F700 TYPE 2 DIABETES MELLITUS - POOR CONTROL

C10F900 TYPE 2 DIABETES MELLITUS WITHOUT COMPLICATION
 C10FA00 TYPE 2 DIABETES MELLITUS WITH MONONEUROPATHY
 C10FB00 TYPE 2 DIABETES MELLITUS WITH POLYNEUROPATHY
 C10FC00 TYPE 2 DIABETES MELLITUS WITH NEPHROPATHY
 C10FD00 TYPE 2 DIABETES MELLITUS WITH HYPOGLYCAEMIC COMA
 C10FE00 TYPE 2 DIABETES MELLITUS WITH DIABETIC CATARACT
 C10FF00 TYPE 2 DIABETES MELLITUS WITH PERIPHERAL ANGIOPATHY
 C10FG00 TYPE 2 DIABETES MELLITUS WITH ARTHROPATHY
 C10FH00 TYPE 2 DIABETES MELLITUS WITH NEUROPATHIC ARTHROPATHY
 C10FJ00 INSULIN TREATED TYPE 2 DIABETES MELLITUS
 C10FK00 HYPEROSMOLAR NON-KETOTIC STATE IN TYPE 2 DIABETES MELLITUS
 C10FL00 TYPE 2 DIABETES MELLITUS WITH PERSISTENT PROTEINURIA
 C10FL11 TYPE II DIABETES MELLITUS WITH PERSISTENT PROTEINURIA
 C10FM00 TYPE 2 DIABETES MELLITUS WITH PERSISTENT MICROALBUMINURIA
 C10FN00 TYPE 2 DIABETES MELLITUS WITH KETOACIDOSIS
 C10FP00 TYPE 2 DIABETES MELLITUS WITH KETOACIDOTIC COMA
 C10FQ00 TYPE 2 DIABETES MELLITUS WITH EXUDATIVE MACULOPATHY
 C10y100 DIABETES MELLITUS, ADULT, + OTHER SPECIFIED MANIFESTATION
 C10z100 DIABETES MELLITUS, ADULT ONSET, + UNSPECIFIED COMPLICATION

Acute Myocardial Infarction

323..00 ECG: MYOCARDIAL INFARCTION
 3233.00 ECG: ANTERO-SEPTAL INFARCT
 3234.00 ECG:POSTERIOR/INFERIOR INFARCT
 3235.00 ECG: SUBENDOCARDIAL INFARCT
 3236.00 ECG: LATERAL INFARCTION
 323Z.00 ECG: MYOCARDIAL INFARCT NOS
 889A.00 DIAB MELLIT INSULIN-GLUCOSE INFUS ACUTE MYOCARDIAL INFARCT
 G30..00 ACUTE MYOCARDIAL INFARCTION
 G30..13 CARDIAC RUPTURE FOLLOWING MYOCARDIAL INFARCTION (MI)
 G30..15 MI - ACUTE MYOCARDIAL INFARCTION
 G30..17 SILENT MYOCARDIAL INFARCTION
 G300.00 ACUTE ANTEROLATERAL INFARCTION
 G301.00 OTHER SPECIFIED ANTERIOR MYOCARDIAL INFARCTION
 G301000 ACUTE ANTEROAPICAL INFARCTION
 G301100 ACUTE ANTEROSEPTAL INFARCTION
 G301z00 ANTERIOR MYOCARDIAL INFARCTION NOS
 G302.00 ACUTE INFEROLATERAL INFARCTION
 G303.00 ACUTE INFEROPOSTERIOR INFARCTION
 G304.00 POSTERIOR MYOCARDIAL INFARCTION NOS
 G305.00 LATERAL MYOCARDIAL INFARCTION NOS
 G306.00 TRUE POSTERIOR MYOCARDIAL INFARCTION
 G307.00 ACUTE SUBENDOCARDIAL INFARCTION
 G307000 ACUTE NON-Q WAVE INFARCTION
 G308.00 INFERIOR MYOCARDIAL INFARCTION NOS
 G309.00 ACUTE Q-WAVE INFARCT

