G30..00 Acute myocardial infarction
G300.00 Acute anterolateral infarction
G30..11 Attack - heart
G30..12 Coronary thrombosis
G30..14 Heart attack
G30..15 MI - acute myocardial infarction
G30..16 Thrombosis - coronary
G30..17 Silent myocardial infarction
G301.00 Other specified anterior myocardial infarction
G301000 Acute anteroapical infarction
G301100 Acute anteroseptal infarction
G301z00 Anterior myocardial infarction NOS
G302.00 Acute inferolateral infarction
G303.00 Acute inferoposterior infarction
G304.00 Posterior myocardial infarction NOS
G305.00 Lateral myocardial infarction NOS
G306.00 True posterior myocardial infarction
G307.00 Acute subendocardial infarction
G307000 Acute non-Q wave infarction
G307100 Acute non-ST segment elevation myocardial infarction
G308.00 Inferior myocardial infarction NOS
G309.00 Acute Q-wave infarct
G30B.00 Acute posterolateral myocardial infarction
G30X.00 Acute transmural myocardial infarction of unspecif site
G30X000 Acute ST segment elevation myocardial infarction
G30y.00 Other acute myocardial infarction
G30y000 Acute atrial infarction
G30y100 Acute papillary muscle infarction
G30y200 Acute septal infarction
G31y100 Microinfarction of heart

G30yz00	Other acute myocardial infarction NOS
G30z.00	Acute myocardial infarction NOS
G30A.00	Mural thrombosis
G5yy600	Atrial thrombosis
G5yy700	Left ventricular thrombosis
G5yy800	Right ventricular thrombosis
14A3.00	H/O: myocardial infarct <60
14A4.00	H/O: myocardial infarct >60
14AH.00	H/O: Myocardial infarction in last year
3232.00	ECG: old myocardial infarction
G32..00	Old myocardial infarction
G32..11	Healed myocardial infarction
G32..12	Personal history of myocardial infarction
G30..13	Cardiac rupture following myocardial infarction (MI)
G310.00	Postmyocardial infarction syndrome
G310.11	Dressler's syndrome
G35..00	Subsequent myocardial infarction
G350.00	Subsequent myocardial infarction of anterior wall
G351.00	Subsequent myocardial infarction of inferior wall
G353.00	Subsequent myocardial infarction of other sites
G35X.00	Subsequent myocardial infarction of unspecified site
G36..00	Certain current complication follow acute myocardial infarct
G36..00	Certain current complication follow acute myocardial infarct
G360.00	Haemopericardium/current comp folow acut myocard infarct
G361.00	Atrial septal defect/curr comp folow acut myocardal infarct
G362.00	Ventric septal defect/curr comp fol acut myocardal infarctn

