 G34y000 Chronic coronary insufficiency
 G1yz100 Rheumatic left ventricular failure
 SP11111 Heart failure as a complication of care
 SP11200 Cardiorespiratory failure as a complication of care
 SP11100 Cardiac insufficiency as a complication of care
 P6yy200 Congenital cardiomegaly
 Q48y100 Congenital cardiac failure
 Q490.00 Neonatal cardiac failure
 14A6.00 H/O: heart failure
 14AM.00 H/O: Heart failure in last year

Peripheral Vascular Disease

RG73..00 Other peripheral vascular disease
 RG73..11 Peripheral ischaemic vascular disease
 RG73..12 Ischaemia of legs

RG73..13	Peripheral ischaemia
RG731.00	Thromboangiitis obliterans
RG731000	Buerger's disease
RG731100	Presenile gangrene
RG731z00	Thromboangiitis obliterans NOS
RG73y.00	Other specified peripheral vascular disease
RG73y000	Diabetic peripheral angiopathy
RG73y100	Peripheral angiopathic disease EC NOS
RG73y200	Acrocyanosis
RG73y400	Acroparaesthesia - Schultze's type
RG73y600	Acroparaesthesia - unspecified
RG73y700	Erythrocyanosis
RG73y800	Erythromelalgia
RG73y811	Erythralgia
RG73yz00	Other specified peripheral vascular disease NOS
RG73z.00	Peripheral vascular disease NOS
RG73z000	Intermittent claudication
RG73z011	Claudication
RG73z100	Spasm of peripheral artery
RG73zz00	Peripheral vascular disease NOS

Transient Ischemic Attack / Stroke

G63..00	Precerebral arterial occlusion
G63..11	Infarction - precerebral
G63..12	Stenosis of precerebral arteries
G630.00	Basilar artery occlusion
G631.00	Carotid artery occlusion
G631.11	Stenosis, carotid artery
G631.12	Thrombosis, carotid artery
G632.00	Vertebral artery occlusion
G634.00	Carotid artery stenosis
G63y.00	Other precerebral artery occlusion
G63y000	Cerebral infarct due to thrombosis of precerebral arteries
G63y100	Cerebral infarction due to embolism of precerebral arteries
G63z.00	Precerebral artery occlusion NOS
G64..00	Cerebral arterial occlusion
G64..11	CVA - cerebral artery occlusion
G64..12	Infarction - cerebral
G64..13	Stroke due to cerebral arterial occlusion
G640.00	Cerebral thrombosis
G640000	Cerebral infarction due to thrombosis of cerebral arteries
G641.00	Cerebral embolism
G641.11	Cerebral embolus
G641000	Cerebral infarction due to embolism of cerebral arteries
G64z.00	Cerebral infarction NOS
G64z.11	Brainstem infarction NOS
G64z.12	Cerebellar infarction
G64z000	Brainstem infarction
G64z100	Wallenberg syndrome
G64z111	Lateral medullary syndrome

G64z200	Left sided cerebral infarction
G64z300	Right sided cerebral infarction

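### The code lists for the two contraindications added in January 2008 are inconsistent within and between countries, and their gaps can only lower the count of contraindicated use

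*Protocol*

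**What the plan says.** The protocol's background states: "In January 2008, EMA added contraindications for rosiglitazone to its label". Section 3.6.2 builds its minimum analysis on that change: use by patients with the "additional contraindications (ischemic heart disease and/or peripheral vascular disease) listed in the 2008 press release", before and after publication. The same sentence brings in prior liver disease, ischaemic heart disease, cardiac failure and acute coronary syndrome. It does not mention infarction. Section 3.4.1 lists prior infarction, prior acute coronary syndrome and peripheral vascular disease as separate conditions, each to be ascertained before the first rosiglitazone prescription. Section 3.4 refers the reader to Appendix 1 for all relevant codes.

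Appendix 1 contains the following.

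- **UK, peripheral vascular disease:** 23 codes, one of them "Diabetic peripheral angiopathy".
- **UK, diabetes:** among many others, "C107.00 DIABETES MELLITUS WITH PERIPHERAL CIRCULATORY DISORDER" and "C10FF00 TYPE 2 DIABETES MELLITUS WITH PERIPHERAL ANGIOPATHY".
- **UK, coronary disease:** there is no list for ischaemic heart disease. The coronary codes, including infarction and one for acute coronary syndrome, sit in the list named Any Cardiovascular Disease. Past-infarction codes such as "H/O: myocardial infarct >60" are there too. A separate list covers acute myocardial infarction.
- **Denmark:** the row beginning "Ischemic heart disease (acute and chronic" holds 411-414 / I20, I24, I25. Infarction has its own row, 410 / I21-I23. Peripheral vascular disease is 440-445 / I70-I74, I77. Acute coronary syndrome has no row.

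**The concern.** These lists decide who counts as a contraindicated user. If a code that names the disease is left off, a patient who has only that code is counted as not contraindicated. Three features suggest that this happens. The UK vascular list accepts one term for diabetic angiopathy and leaves out near-synonyms. The Danish ischaemic heart disease row excludes infarction, and nothing in 3.6.2 clearly brings it back. The UK infarction list lacks the codes by which a past infarction would be recorded. At stake are the level of contraindicated use in the minimum analysis and the comparability of two countries whose proportions are to be reported side by side.

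**Working it through.** The protocol gives no prevalence or code frequency for these conditions, so there is no stated figure to reproduce. The check compares the lists as sets.

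**Step 1, UK peripheral vascular disease.** The UK Diabetes list contains 18 distinct codes that name peripheral circulatory disorder, peripheral angiopathy, gangrene or ischaemic foot ulcer:

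| Group | Codes | Number |
|---|---|---|
| Circulatory disorder | C107.00, C107100, C107400, C107z00 | 4 |
| Angiopathy | C109F00, C109F11, C109F12, C10FF00 | 4 |
| Ischaemic ulcer | M271000 | 1 |
| Gangrene | C107.11, C107.12, C107200, C109500, C109511, C10F500, R054200, R054300 | 8 |
| Angiopathy, also in the vascular list | G73y000 | 1 |

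The 23 vascular codes are printed with a leading R (RG73...). With the R dropped, 1 of 18 matches (G73y000). The other 17 are only under Diabetes: 4 + 4 + 1 = 9 core codes and 8 gangrene codes. Taken literally with the R, 0 of 18 match. The R may come from printing or text extraction, so it should be checked, but nothing here rests on it.

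**Step 2, Danish peripheral vascular disease.** The row has no diabetes-chapter code. Diabetes with organ damage (E10.2-E10.8, E11.2-E11.8 and the ICD-8 codes 249.01-249.05, 249.08, 250.01-250.05, 250.08) appears only in the Charlson table.

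**Step 3, Danish ischaemic heart disease.** {411-414} and {410} share no code, nor do {I20, I24, I25} and {I21, I22, I23}. Together they make 410-414 / I20-I25. Of the conditions named in 3.6.2, only acute coronary syndrome could bring infarction in, and it has no Danish row. In the UK, infarction codes sit with the other coronary codes.

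**Step 4, UK past infarction.** 14A3, 14A4, 14AH, 3232 and the G32 codes are in Any Cardiovascular Disease and not in the acute infarction list. If the latter is used for prior infarction (3.4.1) or to screen out prior events (3.4.3), an infarction recorded only by one of these codes is missed.

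**Step 5, direction.** Adding a code to a list can add patients and cannot remove any. The omissions therefore act one way, towards fewer contraindicated users.

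**Step 6, before and after 2008.** Let true proportions be p1 and p2, and let the lists capture a share s in both periods. The observed values are s·p1 and s·p2. The ratio p2/p1 is unchanged, and the difference shrinks by the factor s. The ratio is distorted only if s differs between periods. A different s in each country does affect the comparison of levels between countries.

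**Step 7, scale, for illustration only.** The user counts, about 20,000 (UK) and 2,400 (Denmark), are from section 3.3. The other inputs are assumptions.

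- UK: vascular disease in 5-10% of users, 10-50% of them coded only in the diabetes chapter. 20,000 × 0.05 × 0.10 = 100, up to 20,000 × 0.10 × 0.50 = 1,000 missed.
- Denmark: prior infarction in 5-10% of users, 10-40% of them without an I20, I24 or I25 code. 2,400 × 0.05 × 0.10 = 12, up to 2,400 × 0.10 × 0.40 = 96 missed.

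The ranges are as wide as the assumptions behind them. They apply to each condition alone.

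**The case against.** The strongest reply is that the protocol recovers most of these patients elsewhere.

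- Section 3.6.2 also promises, without condition, the number and proportion of users with any contraindication defined in the Methods, and 3.4.1 includes infarction. A reader might infer that Danish infarction drops out of the contraindication analysis altogether, or that the 2008 comparison is the only such analysis guaranteed. Neither is so. The gap is confined to the before/after group.
- Acute coronary syndrome could be assembled from the Danish rows with infarction included. That would close the gap, but the protocol does not say so. The objection shows that the definition is open, not that it is sound.
- The UK past-infarction codes are already in Any Cardiovascular Disease, so those patients can enter the UK ischaemic heart disease group. They are also rightly absent from an acute endpoint. The problem arises only if the acute list doubles as the history list, which the protocol neither states nor excludes.
- The UK vascular list does contain diabetic angiopathy, claudication and leg ischaemia. A reader might infer that vascular disease in diabetics is filed only as diabetes, or that typical cases are missed. The first is contradicted by the list. The second cannot be shown, because no code frequencies are given and a patient may carry a listed code as well.
- Changing the UK list alone would create a new mismatch with Denmark. This is correct, and the repair must cover both countries.

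What the reply does not explain is why diabetic peripheral angiopathy counts as peripheral vascular disease while type 2 diabetes with peripheral angiopathy does not.

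**Conclusion.** The point holds in limited form and should be corrected before data are abstracted. Appendix 1 fixes the codes, so this is not a detail left to a later analysis plan. As written, nine UK codes for diabetic peripheral vascular disease do not count as that disease. Denmark has no diabetes-chapter counterpart. On a literal reading, a Danish patient with infarction only is outside the before/after-2008 group, while a UK patient with the same history has a code among the coronary codes. The UK past-infarction gap is conditional on which list is used.

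The direction is certain for these omissions and the size is not. Each omission costs the combined ischaemic heart/peripheral vascular group no more patients than it costs the single condition, and fewer wherever another qualifying code is recorded. A reader might also infer that the measured change at 2008 is biased. The documents do not support that, since the same lists apply before and after and nothing shows that capture shifted.

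**What to change.** 1. Let the nine UK codes count both as diabetes and as peripheral vascular disease. Treat the Danish codes for diabetes with circulatory complications (those within E10.2-E10.8 / E11.2-E11.8 and their ICD-8 equivalents) in the same way. Report the eight gangrene codes as a sensitivity set.
2. In 3.6.2, define ischaemic heart disease as 410-414 / I20-I25 in Denmark and as the matching coronary codes from Any Cardiovascular Disease in the UK. State which Danish codes make up acute coronary syndrome.
3. Use 14A3, 14A4, 14AH, 3232 and G32 for prior infarction and for first-onset screening only, never as an acute event.
4. Check whether the leading R in the UK vascular codes is real.

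The cost is an edit to Appendix 1 and a sentence or two in 3.6.2. The UK codes are already printed in the protocol, and the Danish ones lie within ranges that it prints. The price is a small loss of specificity, and reported contraindicated use will be higher.

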 G30X.00 ACUTE TRANSMURAL MYOCARDIAL INFARCTION OF UNSPECIF SITE
 G30y.00 OTHER ACUTE MYOCARDIAL INFARCTION
 G30y000 ACUTE ATRIAL INFARCTION

G30y100 ACUTE PAPILLARY MUSCLE INFARCTION
 G30y200 ACUTE SEPTAL INFARCTION
 G30yz00 OTHER ACUTE MYOCARDIAL INFARCTION NOS
 G30z.00 ACUTE MYOCARDIAL INFARCTION NOS
 G35..00 SUBSEQUENT MYOCARDIAL INFARCTION
 G31y100 MICROINFARCTION OF HEART
 G350.00 SUBSEQUENT MYOCARDIAL INFARCTION OF ANTERIOR WALL
 G351.00 SUBSEQUENT MYOCARDIAL INFARCTION OF INFERIOR WALL
 G35X.00 SUBSEQUENT MYOCARDIAL INFARCTION OF UNSPECIFIED SITE
 G30..11 Attack - heart
 G30..12 Coronary thrombosis
 G30..14 Heart attack
 G30..16 Thrombosis - coronary
 G30A.00 Mural thrombosis
 G5yy600 Atrial thrombosis
 G5yy700 Left ventricular thrombosis
 G5yy800 Right ventricular thrombosis
 G307100 Acute non-ST segment elevation myocardial infarction
 G30B.00 Acute posterolateral myocardial infarction
 G30X000 Acute ST segment elevation myocardial infarction
 G38..00 POSTOPERATIVE MYOCARDIAL INFARCTION
 G380.00 POSTOPERATIVE TRANSMURAL MYOCARDIAL INFARCTION ANTERIOR WALL
 G381.00 POSTOPERATIVE TRANSMURAL MYOCARDIAL INFARCTION INFERIOR WALL
 G384.00 POSTOPERATIVE SUBENDOCARDIAL MYOCARDIAL INFARCTION

Any Cardiovascular Disease

G311.00 Preinfarction syndrome
 G311.11 Crescendo angina
 G311.13 Unstable angina
 G311.14 Angina at rest
 G311100 Unstable angina
 G311200 Angina at rest
 G311300 Refractory angina
 G311400 Worsening angina
 G311500 Acute coronary syndrome
 G311z00 Preinfarction syndrome NOS
 G33..00 Angina pectoris
 G330.00 Angina decubitus
 G330000 Nocturnal angina
 G330z00 Angina decubitus NOS
 G331.00 Prinzmetal's angina
 G331.11 Variant angina pectoris
 G33z.00 Angina pectoris NOS
 G33z000 Status anginosus
 G33z100 Stenocardia
 G33z200 Syncope anginosa
 G33z300 Angina on effort

G33z400 Ischaemic chest pain
G33z600 New onset angina
G33z700 Stable angina
G33zz00 Angina pectoris NOS
Gyu3000 [X] Other forms of angina pectoris
14A5.00 H/O: angina pectoris
14AJ.00 H/O: Angina in last year
662K.00 Angina control
662K000 Angina control - good
662K100 Angina control - poor
662K200 Angina control - improving
662K300 Angina control - worsening
662Kz00 Angina control NOS
8B27.00 Antianginal therapy
G33z500 Post infarct angina
323..00 ECG: myocardial infarction
3233.00 ECG: antero-septal infarct.
3234.00 ECG: posterior/inferior infarct
3235.00 ECG: subendocardial infarct
3236.00 ECG: lateral infarction
323Z.00 ECG: myocardial infarct NOS

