G363.00	Ruptur cardiac wall w/out haemopericard/cur comp fol ac MI
G364.00	Ruptur chordae tendinae/curr comp fol acute myocard infarct
G365.00	Rupture papillary muscle/curr comp fol acute myocard infarct
G366.00	Thrombosis atrium,auric append&vent/curr comp foll acute MI
Gyu3500	[X] Subsequent myocardial infarction of other sites
Gyu3600	[X] Subsequent myocardial infarction of unspecified site
G38..00	Postoperative myocardial infarction
G380.00	Postoperative transmural myocardial infarction anterior wall
G381.00	Postoperative transmural myocardial infarction inferior wall
G382.00	Postoperative transmural myocardial infarction other sites
G383.00	Postoperative transmural myocardial infarction unspec site
G384.00	Postoperative subendocardial myocardial infarction
G38z.00	Postoperative myocardial infarction, unspecified
ZV71900	[V]Observation for suspected myocardial infarction
889A.00	Diab mellit insulin-glucose infus acute myocardial infarct
G312.00	Coronary thrombosis not resulting in myocardial infarction
G311000	Myocardial infarction aborted
G311011	MI - myocardial infarction aborted
792..00	Coronary artery operations
792..11	Coronary artery bypass graft operations
7920.00	Saphenous vein graft replacement of coronary artery
7920.11	Saphenous vein graft bypass of coronary artery
7920000	Saphenous vein graft replacement of one coronary artery
7920100	Saphenous vein graft replacement of two coronary arteries
7920200	Saphenous vein graft replacement of three coronary arteries

7920300	Saphenous vein graft replacement of four+ coronary arteries
7920y00	Saphenous vein graft replacement of coronary artery OS
7920z00	Saphenous vein graft replacement coronary artery NOS
7921.00	Other autograft replacement of coronary artery
7921.11	Other autograft bypass of coronary artery
7921000	Autograft replacement of one coronary artery NEC
7921100	Autograft replacement of two coronary arteries NEC
7921200	Autograft replacement of three coronary arteries NEC
7921300	Autograft replacement of four or more coronary arteries NEC
7921y00	Other autograft replacement of coronary artery OS
7921z00	Other autograft replacement of coronary artery NOS
7922.00	Allograft replacement of coronary artery
7922.11	Allograft bypass of coronary artery
7922000	Allograft replacement of one coronary artery
7922100	Allograft replacement of two coronary arteries
7922200	Allograft replacement of three coronary arteries
7922300	Allograft replacement of four or more coronary arteries

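### The UK acute myocardial infarction list includes three codes for thrombosis in a heart chamber, so non-infarctions would count towards a named 45-day safety outcome

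*Protocol*

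**What the plan says.** Protocol section 3.4 refers to Appendix 1 for all diagnostic, drug and laboratory codes. Section 3.4.3 names acute myocardial infarction among six events to be examined at the least after a switch to or from rosiglitazone, and requires first occurrences. Section 3.6.3 counts events within 45 days of baseline and estimates adjusted risk ratios.

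In Appendix 1, the UK list headed Acute Myocardial Infarction contains:
- three chamber-thrombosis codes: "G5yy600 Atrial thrombosis", "G5yy700 Left ventricular thrombosis" and "G5yy800 Right ventricular thrombosis";
- "G30A.00 Mural thrombosis";
- "G30..17 SILENT MYOCARDIAL INFARCTION";
- six ECG codes, starting with "323..00 ECG: MYOCARDIAL INFARCTION".

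The code G366.00, worded "Thrombosis atrium,auric append&vent/curr comp foll acute MI", is not in that list. It appears only under Any Cardiovascular Disease. The Danish table defines acute myocardial infarction as ICD-8 410 and ICD-10 I21, I22 and I23.

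**The concern.** The G5yy codes describe a thrombus in an atrium or ventricle. Their terms do not mention infarction, and the codes lie outside the G30, G35 and G38 stems that hold nearly all of the list's infarction codes. A patient with only such a record in the 45 days after a switch would be counted as a new acute myocardial infarction.

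Two things are at stake. First, an outcome chosen because cardiovascular effects are the main safety concern for this drug would include some events that are something else. Second, the outcome would carry one name but two definitions, which weakens any side-by-side reading of the Danish and UK results.

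**Working it through.** The protocol gives no event count, infarction rate, code-level frequency or expected risk ratio, so there is no figure to reproduce. The check compares the lists and then asks what false events could do to the ratio.

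**1. The code lists side by side**

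| Item | UK acute MI list | UK Any Cardiovascular Disease list | Danish acute MI definition |
|---|---|---|---|
| G5yy600, G5yy700, G5yy800 (chamber thrombosis, no infarct named) | yes | yes | no such entry |
| G366.00 (chamber thrombosis after acute infarct) | no | yes | no separate entry |
| G30A.00 (mural thrombosis, under the G30 stem) | yes | yes | no such entry |
| G30..17 and six 323 ECG codes | yes | yes | no such entry |
| 3232.00 (ECG, old infarct) | no | yes | no such entry |

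The UK acute list thus takes in chamber thrombosis that is not tied to an infarct and leaves out the code that is tied to one.

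**2. Count**

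The UK acute list has 52 distinct codes. The three clear mismatches are 3/52 = 5.8% of codes. With G30A.00 (1), silent infarction (1) and ECG (6), 3 + 1 + 1 + 6 = 11 codes need a decision. A share of codes is not a share of events.

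**3. Effect on the risk ratio (illustration under assumed inputs)**

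Let f be the share of recorded infarctions in the comparison group that are false. Let k be the risk of a false record among switchers divided by that risk in the comparison group. Then

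RR_obs = RR_true × (1 − f) + k × f, so RR_obs − RR_true = f × (k − RR_true).

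The bias is downward if k is below RR_true and upward if k is above it. The documents give none of f, k or RR_true. The values below are assumptions that show the range.

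| RR_true | k | f = 5% | f = 10% | f = 20% |
|---|---|---|---|---|
| 1.0 | 0.5 | 0.975 | 0.95 | 0.90 |
| 1.0 | 1 | 1.00 | 1.00 | 1.00 |
| 1.0 | 2 | 1.05 | 1.10 | 1.20 |
| 1.4 | 0.5 | 1.355 | 1.31 | 1.22 |
| 1.4 | 1 | 1.38 | 1.36 | 1.32 |
| 1.4 | 2 | 1.43 | 1.46 | 1.52 |

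For example, with RR_true 1.4, k = 2 and f = 10%: 1.4 × 0.9 + 2 × 0.1 = 1.46. With k = 1 and f = 5% the shift is only 0.05 × (1 − 1.4) = −0.02.

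**The case against.** **The SAP.** Appendix 1 is a list for data abstraction, and an outcome-specific case definition could sit in an SAP that is not shown. This carries limited weight: section 3.4 sends the reader to Appendix 1 for the endpoint codes, and the three terms do not fit the heading they stand under.

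**Different coding systems.** Some difference between READ-coded general practice records and ICD-coded Danish registries cannot be avoided, and section 3.6.3 states no pooled estimate. That stands, but these three codes are an avoidable part of the difference.

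**Silent and ECG codes.** A reader might infer that these contaminate the outcome in the same way. The documents do not support that. They are infarction terms, and the list already leaves out "ECG: old myocardial infarction" and the healed and history-of-infarct codes. Section 3.4.3 also screens out earlier events and, for the UK, looks for pre-existing events in the GPRD Event File. What remains is a dating question: an earlier infarct that was never recorded could be dated to its detection. Dropping these codes could also lose true infarcts coded only that way. Mural thrombosis sits under the G30 stem and is arguable in either direction.

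**Direction.** A reader might also infer that the risk ratio is pulled towards 1. That needs false events equally likely in both groups. Detection prompted by a treatment change would be linked to exposure, and section 3.6.4 itself suggests that recent triggering events may reflect perceived patient risk.

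**Importance and absolute risk.** The protocol ranks no outcome as primary, so acute myocardial infarction is one of six minimum events and not a designated key outcome. Nor is the net effect on the event count known: the same list omits infarction codes that stand only in the broader list (G353.00, G382.00, G383.00 and G38z.00).

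**Conclusion.** The point holds for three codes. G5yy600, G5yy700 and G5yy800 do not describe infarction, yet the protocol counts them as acute myocardial infarction in the UK. This is a minor defect in outcome specificity and in comparability between the countries.

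Its size is 3 of 52 codes. The share of events is unknown until the data are counted. The direction of the bias is also unknown, since it depends on k against RR_true, and the ratios in the table rest wholly on assumed inputs. The silent-infarction, ECG and mural thrombosis codes are a judgement between sensitivity and specificity and call for a sensitivity analysis, not removal.

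**What to change.** - Delete G5yy600, G5yy700 and G5yy800 from the UK acute myocardial infarction outcome list. They remain under Any Cardiovascular Disease.
- Keep G30A.00, G30..17 and the six 323 ECG codes in the main definition, and repeat the 45-day analysis without them as a sensitivity analysis. The recorded date may be that of detection and not of onset, and the G30A.00 term does not itself name an infarct.

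The cost is an edit to one code list, slightly fewer counted events and one extra analysis.
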